8.0 Study Endpoints

8.1 Covariates. Baseline assessment will include a sociodemographic and health questionnaire and questions about previous use of opioids. A literacy assessment using the Newest Vital Sign (NVS) will be performed.

Primary Endpoint. Demonstrated understanding of how to properly dose the opioid medication as measured by participants' ability to correctly dose their prescription regimen using a demonstrated dosing exercise previously used in studies by both Drs. [name] and [name]. Primary endpoint will be assessed at the 7-14 day phone interview.

Secondary Endpoint. Actual use of the opioid medication as measured through the review of the medication diary, participant report of refills and new opioid prescriptions received patient opinion of the intervention as measured by both closed and open-ended questions at the time of follow-up phone interview; patient risky-behaviors while on opioids, as measured by patient self-report. Other aspects of safe use related to *risk awareness* will be assessed using a questionnaire, as will beliefs about medication use. The questionnaire will assess topics including safe storage of opioids, sharing of opioids, disposal on completion of the prescription, and questions related to possible dangerous behaviors. Secondary endpoints will be assessed with phone interviews .

Tertiary Endpoints. The identification of medication names, dosage, risks, warnings, and benefits will be assessed through a structured questionnaire that has been developed and used extensively by [name] and colleagues in multiple studies and current NIH-funded grants. The self-report of provider counseling will also be measured. Tertiary endpoint assessments will be assessed via phone interviews.

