The initial study visit (baseline) will be conducted at the time of patient enrollment. Following this baseline interview, RAs will conduct three telephone interviews (at 2-4 days post-baseline, 7-14 days post-baseline and at one month post-baseline). The first two assessments (at enrollment and 2-4day follow-up call) have been included to closely track patient recall of counseling and knowledge, while the latter two assessments (7-14 day follow-up call and 1 month follow-up call) are included to assess decay of knowledge, safe use, storage of medications and demonstrated dosing. The final call (one month post-baseline) will assess disposal of

EHR-Based Medication Complete Communication (EMC²) Strategy to Promote Safe Opioid Use: A Physician Randomized Trial

medications and determine if patients have received additional opioid pain relievers from other providers.

Baseline Interview. At the time of enrollment, the RA will ask the participant to indicate the best days and times to call within a 2-4 day range. A \$5 Gift card given to the participant for completion of enrollment tasks.

First Study (2-4 Day) Phone Call. The study phone call will be conducted at a time of convenience for the patient, however still within a 2-4 day range post-baseline. Additionally during this phone call, the RA will either confirm or schedule the 7-14 day follow-up call. A \$10 Gift card will be mailed to the participant for completion of first phone call.

Second Study (7-14 Day) Phone Call. The second phone call will be conducted at a time of convenience for the patient, however still within 7-14 day range post-baseline. Patients will be compensated for their time to complete the call with a \$20 gift card which will be mailed to the participant upon completing the call. Patients will also be asked to mail back their de-identified medication diary using the prepaid envelope provided at baseline.

Third/Final Study (1 Month) Phone Call. The final study phone call will be conducted at a time of convenience for the patient, however still within 1-month post-baseline. (See Attached Interview script)

Intervention Patients with physicians randomized to the EMC² arm will receive the 5-part EMC2 intervention.

[figure not shown]

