11.0 Data and Specimen Management

- 11.1 AIM 1 Analysis Plan. The proposed trial uses a cluster-randomized design where the prescribing physician is the unit of randomization. We will randomize approximately 150 physicians (50 attending physicians, 100 EM resident physicians and mid-level providers) to three intervention arms (usual care, EMC², and EMC² + SMS text reminders). The estimate of 150 includes a base of 100 providers with an estimate of approximately 50 new providers over the course of the 18 months of recruitment (e.g. 15 new residents in 2015, 15 new residents in 2016 and new attending hires). At any given time, we estimate that 100 providers will be actively involved in the study, resulting in approximately 33-34 physicians per arm. Physicians will be stratified by provider role (i.e., attending vs. resident) and randomly assigned to one of the three arms with an equal number assigned to each. We will accrue approximately 12 patients per physician; we conservatively anticipate at least 54% retention for the phone call follow-up 7-14 days post prescription. These estimates will result in 1500 participants recruited with an anticipated

EHR-Based Medication Complete Communication (EMC²) Strategy to Promote Safe Opioid Use: A Physician Randomized Trial

minimum of 816 patients at in-person follow-up (272 per arm, 8 per physician) available for primary data analysis.

To ensure adequate balance across the 3 arms, potential confounders including socio-demographic characteristics, comorbidities, regimen complexity (i.e., # of medications, total pills taken daily), health literacy level, and history of opioid use will be compared using one-way ANOVA models and χ^2 tests, as appropriate. Covariates with significant differences (p -value $< .05$) across treatment groups will be included in the generalized linear mixed models (GLMMs) to adjust for the group differences as described below. We note that detected differences may be physician-specific, so if we observe differences across the treatment arms, we will explore whether the difference might be attributable to individual physicians.

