Demonstrated safe use by not exceeding the maximum dose is the primary outcome of interest for Aim 1 (H_3), with higher reported rates of provider counseling and greater understanding of risks relevant to hypotheses of secondary interest for Aim 1 (H_1, H_2). We will use GLMMs for analyses of the data, specifying the logit link function for the binary outcomes using xtmixed in Stata (v.12.1). The 3-category treatment group variable will be the independent variable of primary interest and modeled as a fixed effect with the usual care group specified as the reference. We will also include fixed effects for any potential confounding covariates noted in the descriptive studies that were not accounted for in randomization. Random effects will be included for each physician to account for intra-physician correlation among participants. For all GLMM analyses we will report point estimates and corresponding 95% confidence intervals. We will examine and report the extent to which the random effects suggest correlation of outcomes within physicians.

Measures taken to minimize bias. For the randomization scheme of this study, physician is the unit of randomization rather than patient. With healthcare interventions and quality improvement projects, such as the one proposed herein, there are no other ways to evaluate an automated EHR process than to “turn them on.” This is why the randomization will occur at the physician level rather than the patient level. This process will result in trickle down of aspects of the EMC² intervention (but not SMS texting) to patients seen by the consented provider, but not enrolled in the study for follow-up purposes (e.g., on overnight shifts).

Level of significance to be used. We will use a two-sided 5% significance test

Stopping rules. We will stop enrollment once we have reached the 1500 patient enrolled maximum.

EHR-Based Medication Complete Communication (EMC²) Strategy to Promote Safe Opioid Use: A Physician Randomized Trial

Procedures for reporting deviations from the original plan. Any deviations involving human subjects will be submitted to the IRB for review before being implemented.

Selection of subjects for inclusion in the analysis. All subjects with complete information (e.g., at least 80% completion of interview instrument) will be used in the analysis.

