13.0 Withdrawal of Subjects

- 13.1 In the case that subjects do not complete their follow-up phone interviews and do not respond to 3 calls attempting to re-schedule, they will be withdrawn from the study. Additionally, if subjects exhibit inappropriate or violent behavior towards research personnel, they will be withdrawn from the study.
- 13.2 If a subject decides to withdraw from the study, there will be instructions in the consent document (all patients provided signed copy) with information regarding contacting the study coordinator or PI to withdraw their consent.

EHR-Based Medication Complete Communication (EMC²) Strategy to Promote Safe Opioid Use: A Physician Randomized Trial

13.3 If a subject withdraws from the study the data collected to that time point will be retained to assess for bias in the final sample. They will not be contacted further for interviews.

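### The 80% interview-completeness rule could drop observed primary outcomes, and no sensitivity analysis is stated for a planned loss of up to 45.6% of them

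*Protocol*

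**What the plan says.** - **Endpoint.** Protocol section 8.1 makes the primary endpoint a demonstrated dosing exercise and fixes its time: "Primary endpoint will be assessed at the 7-14 day phone interview".
- **Who is analysed.** Section 11.1, under selection of subjects: "All subjects with complete information (e.g., at least 80% completion of interview instrument) will be used in the analysis". The interview is not named and the dosing item is not mentioned.
- **Expected loss.** Section 11.1: "we conservatively anticipate at least 54% retention for the phone call follow-up 7-14 days post prescription". It enrols 1500 and expects at least 816 (272 per arm) for the primary analysis. The SAP's closing paragraph likewise sets its target as 816 patients completing the 1-2 week follow-up.
- **SAP approach.** Analyses are labelled intent-to-treat first. The primary outcome is then repeated per-protocol, in patients who received the intervention components. The SAP does not define the first set, mention missing outcomes or refer to the 80% rule.
- **Withdrawal.** Section 13.1 concerns patients who miss their calls, without naming a call; if they also "do not respond to 3 calls attempting to re-schedule, they will be withdrawn from the study". Section 13.3 says that for a subject who withdraws "the data collected to that time point will be retained to assess for bias in the final sample", and ends further interview contact. Section 24.1 keeps patients who cancel the texts in outcome assessment.

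**The concern.** There are two linked problems.

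First, the inclusion rule concerns the completeness of an interview, while the primary endpoint is one exercise within it. A patient may complete the dosing exercise and then stop below 80%. Applied as a filter, the rule discards that observed primary outcome. Because the SAP is silent on the rule, two analysts could build different sets and call both intent-to-treat.

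Second, nearly half the primary outcomes may be missing. Enrolling 1500 to obtain 816 protects power but does nothing about selection. A complete-case logistic mixed model is valid for the conditional odds ratio if missingness depends only on arm and modelled covariates. Covariates are chosen for baseline imbalance (section 11.1) or relation to the outcome (SAP), not for relation to retention. Only one arm receives seven daily texts, so retention could plausibly depend on arm together with unmodelled engagement. Without a comparison of retention by arm or a sensitivity analysis, a reader cannot judge how far the conclusion depends on the missing-data assumption.

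**Working it through.** **Inputs.** From Protocol section 11.1: 1500 enrolled, minimum 816 analysed, 272 per arm. From section 11.2: 11.8-point difference, 82% power, Type I error 2.5% per comparison. From the SAP: 80% power for the same difference, significance at 0.025. Tests are two-sided (section 11.1). Assumed: equal loss by arm, and a difference among completers of exactly the planned 11.8 points.

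**1. The plan's own count.** 1500 × 0.54 = 810, against the stated 816. 3 arms × 34 physicians × 8 patients = 816 exactly, and 816/1500 = 54.4%. The figure reproduces.

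**2. Planned ceiling on loss.** 1500 − 816 = 684, and 684/1500 = 45.6% (228 of 500 per arm). This is a ceiling because 816 is a stated minimum.

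**3. No difference among non-completers.** 11.8 × 816/1500 = 6.4 points over all enrolled.

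**4. One-arm departure δ from missing-at-random.** Let outcomes of the missing patients in one arm be δ points worse than missing-at-random predicts. The all-enrolled difference is then 11.8 − 0.456δ.
- Estimate removed: δ = 11.8/0.456 = 25.9 points.
- Equivalently, non-completers would show a reversed difference of 25.9 − 11.8 = 14.1 points, which matches 11.8 × 816/684 = 14.1.

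**5. Departure at which significance is lost.** The stated power fixes the critical difference on a normal approximation, so no usual-care rate is needed:

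critical difference = 11.8 × z(0.9875) / [z(0.9875) + z(power)], with z(0.9875) = 2.241.

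| Stated power | z(power) | Critical difference | δ = (11.8 − critical)/0.456 |
|---|---|---|---|
| 82% (Protocol) | 0.915 | 11.8 × 2.241/3.156 = 8.38 | 7.5 points |
| 80% (SAP) | 0.842 | 11.8 × 2.241/3.083 = 8.58 | 7.1 points |

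This treats the standard error as unchanged by δ, so the values are approximate.

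**6. Does any stated analysis test this?** The per-protocol analysis restricts further, by receipt of the intervention. The SAP's balance tests address randomisation, not completers against non-completers. The only sensitivity analyses in either document concern Aim 3 costs.

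**The case against.** The strongest replies, and what stands of each:

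- **The primary set is known.** This largely stands. A reader might infer that it is undefined, but section 11.1 and the SAP target both point to patients completing the 7-14 day interview. The ambiguity is narrower: partly completed interviews, and which interview the 80% covers.
- **The rule does not say that an observed outcome is excluded.** Correct. The 80% is given as an example, and exclusion follows only if the sentence is read as a filter. The documents do not show how many outcomes this would affect, and it may be few.
- **The loss is already in the sample size, and data are kept to assess bias.** Both are true. There is no sample-size error here. However, section 13.3 names no method, and the SAP does not take the intention up.
- **The result may be unbiased.** It may. Removing the estimate needs a 25.9-point one-arm shift, and nothing in the documents suggests one.
- **Significance might seem to vanish with a shift of about 5 points.** Scanning assumed usual-care rates does give 4.9 points at a rate of 44.1%. Power at that rate is only about 70%, which does not fit the stated 82% or 80%. The values consistent with the plan are 7.5 and 7.1.
- **The contact rule might seem to cancel the primary interview after a missed 2-4 day call.** Section 9.2 says that at the earlier call "the RA will either confirm or schedule the 7-14 day follow-up call", and section 13.1 names no call. But 13.1 requires both non-completion and non-response to three rescheduling attempts, and 13.3 may cover only patient-initiated withdrawal. No document shows that a primary interview was lost this way. It is a point to clarify, not a defect established.

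**Conclusion.** The concern holds and should be fixed. The completeness rule can be read to exclude observed primary outcomes, and the SAP's label does not settle the matter. The primary result is a complete-case analysis with up to 45.6% of outcomes unobserved and no stated check on that. Under equal loss and the planned effect in completers, a one-arm departure of roughly 7 to 7.5 points would overturn significance, while about 25.9 points would be needed to erase the estimate. So the significance claim is moderately sensitive to the missing-data assumption and the direction of effect much less so. The documents demonstrate neither bias nor differential retention, and do not give the number of partial interviews.

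**What to change.** **(a) Section 11.1 and SAP.** For the primary analysis, replace the 80% rule with: every enrolled patient of a randomised provider who has an observed 7-14 day dosing outcome, analysed as assigned, whatever the completeness of the rest of that interview or of later calls. Describe the set in those words rather than by the intent-to-treat label alone. It remains the primary analysis.

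**(b) SAP.** Report retention, and baseline characteristics of completers and non-completers, by arm. As a sensitivity analysis over all enrolled patients, add multiple imputation that respects provider clustering, with an arm-specific delta increased until the conclusion changes, and report that value. The 1-month call is a natural source for the imputation model, since section 9.2 says that the two later calls "are included to assess decay of knowledge, safe use, storage of medications and demonstrated dosing".

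**(c) Minor clarification.** Report how the section 13.1 contact rule was applied, and whether any patient was not called for the 7-14 day interview because of an earlier missed call.

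**Cost.** Wording and modest programming on data the plan already collects, with no extra patients. The SAP is dated June 2019 and written in the past tense, but (a) and (b) remain possible after follow-up, and (c) may be a report from call records. The downside is that the sensitivity results may be less favourable than the primary result.

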Patients with ED physicians randomized to the EMC² +SMS Text reminder arm will receive the above-described 5 components of the EMC² intervention, and also will receive daily text reminders for one week (7 messages) following the new prescription for an opioid pain reliever (only consented patients). The premise for the 1-week timeframe is to help patients remember precautions regarding safe use during the time they are taking the medication (average ED Rx for opioids is from pilot data is 18 tabs). Furthermore, SMS text reminders that would continue indefinitely are at risk for either being ignored, irritating patients, and/or adding an unnecessary expense to patients (i.e., patient does not have an unlimited texting plan, further challenging sustainability). Messages sent early in the week will focus on topics such as safe storage and use; those sent near the end of the week will focus on topics such as disposal and pill sharing. We will schedule EMC² text messages to arrive mid-day (12:00pm to 5:00pm), based on patient preference. (See appendix for sample text messages)

9.3 Procedures to monitor safety and minimize risk.

As a part of all of the time points of follow-up, the RAs will have a checklist of potentially dangerous behaviors related to opioids and if these items are noted in the course of data collection the RAs have a set protocol to follow. (see safety protocol attached)

9.4 The drug hydrocodone-acetaminophen is the topic of the research; however it is not being used in the research—the intervention is focused on education about this medication and the study will not change the drug, dose, frequency, quantity or refills that the ED physician selects in the course of their normal clinical care.

Sources of Materials:

Electronic Health Record (EHR): Patient information and outcomes will be extracted from the EHR (demographics, ED return visits and re-admissions). Re-admissions and re-visits to the hospital and ED data will be abstracted from medical records for all patients enrolled into the study, as well as all patients prescribed an opioid during the recruitment period of 18-months.

EHR-Based Medication Complete Communication (EMC²) Strategy to Promote Safe Opioid Use: A Physician Randomized Trial

Illinois Prescription Monitoring Program (ILPMP): We will obtain data from the ILPMP on medication fill date, subsequent refills of the prescribed opioid, and new prescriptions for other controlled substances.

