AIM 2 Analysis Plan. Following completion of enrollment, we will determine the extent to which the interventions were implemented as planned (a process evaluation) in the two intervention arms. In the EMC² and EMC² + SMS text reminder arms, we will collect EHR data on prescriptions and discharge summaries to assess if patients actually received the new prescriptions with the UMS (Take-Wait-Stop) sig, and review pill bottle information during the 7-14 day phone call to determine if the sigs were translated accordingly onto patients' drug labels. For the EMC² + SMS text reminder arm, we will ask patients at all follow-up intervals if they received the text messages. For those electing to turn off the service, we will qualitatively explore and code reasons why.

Usability of the EHR interventions will be assessed among the ED physicians and follow-up providers (PCPs and pharmacists) via survey.

AIM 3 Analysis Plan. We will directly measure and assess the provider perspective costs of running the two EMC² interventions. Specifically, we will estimate the incremental cost of the interventions relative to usual care from the perspective of the ED implementing these systems. The primary costs of running the EMC² intervention involve the limited expenses around printing (printer ink, paper, staff time). However, we will include estimates for minimal programming maintenance and will test the sensitivity of results to changes in the maintenance requirements in terms of programmer hours. We also will separately track development costs for software and other programming requirements based on programmer hours. The greater cost, in terms of running the program, will be that for the SMS text services, which will include the nominal monthly cost as well as staff time to schedule the SMS text reminders after the initial ED visits. For study purposes, the RA will do this task; however, we will have record on a daily basis in a study database (Microsoft Office Access, Microsoft Corp.) the number of minutes spent programming the SMS text reminders. This record will allow us to estimate the direct staff costs of this component by combining time with wage estimates. We will test the sensitivity of costs to different assumptions about the potential use of variable staff (nurse, clerk, medical assistant) using different salaries but assuming the same proficiency in terms of time required. Further we will assess the sensitivity of the

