14.0 Risks to Subjects

14.1 Patients who receive care at the participating Emergency Department during this study will be subject to minimal risk through their participation. It is possible that subjects may feel shame and/or some emotional discomfort when taking the literacy and medication use assessments, and performing medication related tasks. We will also be making changes to how their medication instructions are written, and learning through follow-up interviews how they are implementing regimens. If we find that patients in any study arm are misusing medications, we will have a structure in place to address these concerns. This will be documented accordingly within internal study documents; however will not become a part of the medical record unless patients require acute care for their drug misuse or abuse. Consent forms will also acknowledge this disclosure.

Patients in one study arm will receive automated text messages that some could view as intrusive; however they will have the ability to opt-out of the messages at any time. With SMS texting via cell phones, only the phone number is entered into the automated texting system, and no other patient information. We will uphold patient confidentiality and respect any requests to turn off this function during the study.

Subjects will be informed that participation in any part of this research study may result in a loss of privacy, since persons other than the investigators may view their study records if deemed necessary for oversight purposes. However, they will be identified by a unique identification number (“study number”), not by name, and any other identifying information (e.g. personal and/or contact information) will be kept separate from the other data; All information will be kept in secure, password protected files. Further, subjects will be told that unless required by law, only the study investigators, members of the project staff, and representatives of the Northwestern University or clinic Institutional Review Boards will have the authority to review any study records. In such case, they too will be required to maintain confidentiality.

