Statistical Analysis Plan

EHR-Based Medication Complete Communication Strategy to Promote Safe Opioid Use

NCT02431793

Document Date: June 7, 2019

Analysis Plan – Main Manuscript

Descriptive statistics were calculated for all socio-demographic, ED visit, and opioid prescription characteristics. Chi-square, one-way Analysis of Variance (ANOVA), and Wilcoxon rank-sum tests were used, as appropriate, to test for balanced randomization. An inter-cluster correlation assessment was conducted to assess the degree of independence among individuals in the same cluster. We used generalized linear mixed models on all outcomes adjusting for physician clustering. Models were run for dichotomous outcomes (safe demonstrated dosing, safe actual dosing; adjusted odds ratios [ORs] reported) and for continuous composite knowledge score (adjusted mean differences reported). Examination for possible associations between patient characteristics and outcome variables revealed significant was conducted, and all models controlled for covariates that related to the outcome. To isolate the effect of the SMS texting portion of the intervention from the EMC² EHR embedded tools a generalized linear mixed model was conducted utilizing two dummy variables (“emc2” for patients in both intervention arms, “text” for patients in EMC² +SMS arm) rather than the study arms on the primary and secondary outcomes as well as the individual knowledge or behavior questions linked to each text message. Significance for all analyses was set at $p < 0.025$ to adjust for multiple testing.

All analyses were first conducted using an intent-to-treat approach. Subsequently, because some patients did not receive one or more pieces of the intervention, the primary outcome was analyzed per-protocol, where the same methodology described previously was used but applied only to patients who successfully received all patient-facing pieces of the intervention. Patients in the EMC² arm were included in the per-protocol analysis if they received the MedSheet and the patient-centered TWS prescription wording on their bottle. Those in the EMC² +SMS arm were included in the per-protocol analysis if they received the MedSheet, TWS prescription wording on bottle, successfully enrolled in SMS texting, and received all seven text messages.

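### Text-message fidelity is measured only by asking SMS-arm patients on follow-up calls, and the SAP names no source for its all-seven-texts criterion

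*Protocol*

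**What the plan says.** Aim 2 (Protocol 11.1) is a process evaluation of how far the two interventions were delivered as intended. For the text component it names a single measure: "For the EMC² + SMS text reminder arm, we will ask patients at all follow-up intervals if they received the text messages". It adds that reasons for turning the service off will be explored, without saying how those patients are identified.

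The label component is treated differently in the same paragraph: "we will collect EHR data on prescriptions and discharge summaries to assess if patients actually received the new prescriptions with the UMS (Take-Wait-Stop) sig", supplemented by a check of the pill bottle at the 7-14 day call.

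The texts are sent once a day for a week, seven in all (Protocol 9.2), through an automated service. On that service, Protocol 14.1 says that "only the phone number is entered into the automated texting system, and no other patient information". The only record of SMS work that the protocol describes is staff minutes, kept for the Aim 3 costing.

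The SAP states that, after the intent-to-treat analysis, "the primary outcome was analyzed per-protocol". An SMS-arm patient enters that set only if the patient "received the MedSheet, TWS prescription wording on bottle, successfully enrolled in SMS texting, and received all seven text messages". The SAP does not say where the information on the seven texts comes from.

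**The concern.** The texts are the only component that separates the two intervention arms. The SAP fits a separate model to isolate their effect. If that effect is small, the reader must know whether the messages failed to arrive or arrived and did not help. A call question cannot settle this for the arm: it reaches only those who answer, it depends on memory, and its first asking comes before the series is complete.

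The SAP then needs an exact fact for each patient, receipt of all seven messages. The question in the Aim 2 plan is described as asking whether texts were received, not how many. So the one measure the protocol describes does not clearly supply what the SAP's rule needs, and no other source is named.

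**Working it through.** **Inputs**
- 1500 patients enrolled, at least 54% retained at the 7-14 day call, 816 available (272 per arm, 8 per physician, about 33-34 physicians per arm): Protocol 11.1, Aim 1.
- Seven texts, one a day for a week: Protocol 9.2.
- Calls at 2-4 days, 7-14 days and 1 month: Protocol 7.0 and 9.0.
- Assumed: equal numbers of patients per arm; first text on day 0 or day 1; a reported-receipt rate *f* among responders of 50%, 70% or 90%. The documents give no fidelity rate.

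**1. The plan's own figure.** 1500 × 0.54 = 810, against the stated 816. The stated figure corresponds to 816/1500 = 54.4%, and it also follows from 34 × 8 = 272 and 3 × 272 = 816. The retention figure is reproduced.

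**2. Patients with no 7-14 day answer.** 1500/3 = 500 per arm. 500 − 272 = 228, and 228/500 = 45.6%.

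**3. Timing.** If the first text goes out on day 0, the seventh goes out on day 6; if on day 1, on day 7. By day 4, the latest day for the first call, at most five texts (days 0 to 4) or four (days 1 to 4) can have been sent. The 7-14 day call is the first that can cover all seven.

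**4. What the missing answers allow.** With 54.4% of the arm answering and a rate *f* among them, the whole-arm rate lies between 0.544*f* (no non-responder received the texts) and 0.544*f* + 0.456 (every one did).

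| *f* (assumed) | Lower bound | Upper bound |
|---|---|---|
| 50% | 27% | 73% |
| 70% | 38% | 84% |
| 90% | 49% | 95% |

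The interval is 46 points wide whatever *f* is. It covers missing answers only; recall error comes on top. One-month answers could narrow it, but no retention figure is given for that call. Protocol 13.1 also withdraws patients who miss interviews and do not respond to three rescheduling attempts, so few are likely to be recovered there.

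**5. The per-protocol criterion.** The outcome in that analysis is the primary one, and "Primary endpoint will be assessed at the 7-14 day phone interview". Every patient who can contribute to it has therefore answered that call. The 228 are absent from it whatever source is used for text receipt, so step 4 applies to the Aim 2 rate and not to the per-protocol set. What remains for the per-protocol set is an unnamed data source.

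**The case against.** The strongest counter-argument is that the documents are silent on a message log and do not reject one. The SAP does not refer to the call question, and enrolment in texting could well come from a study or system record. The interview battery is an attachment that is not available here and may ask more than the protocol describes. The question is repeated at every call, so an early asking does no harm. Section 14.1 is a privacy statement and says nothing about stored delivery data. Patient report also captures something a log cannot: whether the message was noticed.

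Much of this stands, and it rules out three stronger readings that a reader might infer:

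- *That the per-protocol set is built on recall.* The documents do not say so. They leave the source open.
- *That losing non-responders biases the per-protocol set.* It adds no selection there, because the outcome exists only for patients reached at the 7-14 day call.
- *That recall gives the SMS arm a spurious benefit of some calculable size.* Nothing in the documents gives the accuracy of recall or its relation to dosing errors, so any such figure would be invented.

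The objection does not remove the Aim 2 problem. There the measure is stated, it is the only one stated, and it misses nearly half the arm at the first call that can cover all seven texts.

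**Conclusion.** The point holds for Aim 2 fidelity and, more narrowly, as an unspecified source in the SAP. Followed as written, the plan yields a rate of remembered receipt among patients reached. At planned retention and with equal arms, 228 of 500 SMS-arm patients (46%) give no 7-14 day answer, which leaves the whole-arm rate uncertain by 46 points before recall error. Retention above the stated minimum would narrow this.

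For the per-protocol analysis, the supportable statement is only that the all-seven criterion has no named source and that the question described does not count texts. The intent-to-treat analysis is not affected. The consequence is limited to a process measure and a follow-on analysis, but the correction is cheap and worth making.

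**What to change.** - **Protocol, Aim 2 plan:** measure text fidelity for every patient allocated to EMC² + SMS, whether or not reached by phone, from the automated texting system's send, delivery and opt-out record. Link it by phone number to the study ID. The linkage can be done on the study side through the master tracking database (Protocol 11.3), so no further patient information need enter the texting system.
- **SAP:** name that record as the source for the all-seven-texts criterion, and say how opt-outs are classified.
- **Call question:** keep it, reported separately as whether patients noticed or remembered the texts, with the number answering at each call.

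The cost is one export, one linkage step and a sentence or two in each document. The change assumes that the system stores a message record, which the documents do not state; if it holds only sends and opt-outs, use those. Delivery does not prove reading, which is why the question stays.

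The SAP is written in the past tense. If no record can be retrieved, it should state which source was used and label the fidelity rate as self-reported receipt among patients reached.
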